10 STATISTICS AND DATA ANALYSIS

10.1 Sample size calculation

We used an app that was designed to calculate power in multiple single case series studies (Single Case Designs (architecta.shinyapps.io/SingleCaseDesigns v3/). A permutation distance test, which is useful in this design because it corrects for auto-correlation, showed that with sample size of 10 and Cohen's d of 1 the power is close to 1. We are expecting some participants may drop out of the study, and so aim to recruit 14 potential participants.

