10.3.2 Primary outcome analysis

Primary outcome measures are personality functioning, using the LPFS 2.0 scale, and changes in loneliness, using the Social Isolation Short Form 4a. These measures will be filled out on a weekly basis. The line graphs of the data will be inspected visually first, to see the pattern of observations. We will analyse for trend (progress over time), level of change and stability (variability) within the three phases using within-condition and between-condition visual inspection analyses. The median, median regression, stability envelope of the regression and TAU-U (Parker et al. 2011) will be calculated for each phase, with the median level of change chosen to mitigate the influence of outliers in the data. We will test the hypothesis that the median in the baseline phase exceeds the medians of the treatment and follow-up phase. In addition, non-parametric randomisation tests will be used to statistically evaluate the difference in mean and median scores of the phases statistically. The permutation distance test (Vroegindeweij et al. 2023) will be used since this randomisation test corrects for autocorrelation before the permutation test takes place. In this test a p-value is calculated

for every participant. Moreover, a p-value for the group will also be calculated using the property of p-values that they are uniformly distributed under the null-hypothesis. Using this property, the p-value of the group effect is the probability of a series of individual p-values given the null hypothesis (Onghena et all. 2005). In this test a range of baseline lengths, i.e. the number of baseline measurements, is determined and participants are randomly assigned to one of these baseline lengths. In this test a null distribution of 1000 mean differences is calculated and it is counted how many of the random mean differences is as extreme or more extreme than the observed mean difference (Bouwmeester, 2021).

Service use and self-harm data will be compared between the treatment phases with nonparametric test for repeated measures (Friedman Test), depending on the fulfilment of the requirements for parametric test.

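### The 1000-draw permutation null in section 10.3.2 leaves individual p-values near 0.05 dependent on the random seed, and the counting rule should be written as (count + 1)/(permutations + 1)

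*Protocol*

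**What the plan says.** Section 10.3.2 plans visual inspection, phase medians, median regression and Tau-U for the LPFS-BF 2.0 and the Social Isolation Short Form 4a. It then adds the tests at issue: "In addition, non-parametric randomisation tests will be used to statistically evaluate the difference in mean and median scores" between phases. The direction of interest is stated: "We will test the hypothesis that the median in the baseline phase exceeds the medians of the treatment and follow-up phase".

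The p-values work at two levels. One is calculated "for every participant. Moreover, a p-value for the group will also be calculated". The group value is described thus: "the p-value of the group effect is the probability of a series of individual p-values given the null hypothesis". On the mechanics, the section says that "a null distribution of 1000 mean differences is calculated and it is counted how many of the random mean differences is as extreme" as the observed one, or more so.

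The section gives no denominator for the count, no statement on whether the observed arrangement is included, and no formula for combining the individual p-values. The protocol states no significance level. Section 10.1 reports that for 10 participants and a Cohen's "d of 1 the power is close to 1".

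**The concern.** A permutation p-value from a random sample of arrangements is itself an estimate. With 1000 draws its error is large enough, close to a cut-off, for a rerun with another seed to change the verdict. A p-value is produced for each of 10 to 14 participants on two primary measures, so some borderline values should be expected.

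The second issue is the counting rule. A count of random differences alone can be 0, and a permutation p-value of 0 is not valid, because the observed arrangement is always one of the possible ones. Since the individual p-values feed the group value, a zero could matter there, depending on how they are combined.

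**Working it through.** **Inputs.** R = 1000 draws (10.3.2). 8 baseline and 72 treatment scores per participant (Appendix 4). n = 10, d = 1 (10.1). Assumed, because not stated: cut-off 0.05, one-sided test, b/R as the literal reading of the count b, and, where a group p-value is needed, a sum-of-p rule with a product rule as the alternative.

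**The plan's own figure.** Pooling 10 participants gives 80 v 720 scores. At d = 1 the power exceeds 0.999. Simulating ten participants, with 1000 permutations each and a sum-of-p combination, gave group power of 1.00 (120 of 120 trials) under independence and under AR(1) autocorrelation of 0.3 and 0.5 with thinning. The power in section 10.1 is therefore reproduced. Power for a single participant is lower: about 0.85 under independence, 0.59 at autocorrelation 0.3 and 0.48 at 0.5.

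**Monte Carlo error.** SE = sqrt(p(1 − p)/R). At p = 0.05 and R = 1000 this is sqrt(0.05 × 0.95/1000) = 0.0069, a 95% range of 0.0365 to 0.0635. At R = 10,000 it is 0.0022. The chance of reporting the wrong side of 0.05, from the binomial distribution of the count, is:

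| True p | R = 1000 | R = 10,000 |
|---|---|---|
| 0.03 | 0.02% | about 0 |
| 0.04 | 5% | about 0 |
| 0.045 | 20% | 0.8% |
| 0.055 | 27% | 1.4% |
| 0.06 | 10% | about 0 |

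**How often this bites.** In simulations of one participant (8 v 72 scores, d = 1), two runs of the same 1000-draw test disagreed about 0.05 for roughly 2 to 4% of p-values.

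**Group level.** With a sum rule and ten participants, a group p-value exactly at 0.05 has a 95% Monte Carlo range of 0.040 to 0.062 at R = 1000. At d = 1 the group result lies far from that boundary.

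**Zeros, if p = b/1000.**
- Frequency at d = 1: about 27% of individual p-values under independence, 8% at autocorrelation 0.3 keeping every second score, and 4% at 0.5 keeping every third. Further runs with autocorrelation and thinning gave 0 to 7%.
- Size at 0.05: b/1000 gives 51/1001 = 0.0510, and (b + 1)/1001 gives 50/1001 = 0.0500. The smallest attainable p becomes 1/1001 = 0.0010.
- Sum rule: replacing one zero by 1/1001 moves a group p-value from 0.02054 to 0.02060. Adding 1/1001 to all ten moves 0.0500 to 0.0512.
- Product rule (Fisher): the log of zero is minus infinity, so one zero gives a group p-value of 0 whatever the other participants show. In a constructed case of one clear responder and nine unchanged participants, (b + 1)/1001 instead gives a median group p of 0.053.

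**Enumeration.** Keeping every third score leaves 3 v 24 points and 27 × 26 × 25/6 = 2925 arrangements, few enough to list in full. Keeping every second leaves 4 v 36 points and 40 × 39 × 38 × 37/24 = 91,390.

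**The case against.** The strongest reply is that the protocol never writes p = b/1000. It gives no denominator and attributes the step to a cited app, which may already add the observed arrangement. The convention and the seed are details that a statistical analysis plan often carries. The paragraph is also ambiguous: the sentence before the 1000 draws concerns random assignment to baseline lengths, so which test the draws belong to is not beyond doubt. This stands. The zero is a consequence of one literal reading and not something that the protocol states.

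A reader might go further and infer that the group efficacy result is degenerate, because one zero p-value would make it 0. That needs two unstated choices together, b/1000 and a product rule. The wording on the group p-value fits a sum rule as well, and there a zero is harmless. Nor does the high zero rate under independence carry over once autocorrelation, the reason given for choosing this test, is allowed for. At d = 1 the group verdict does not depend on it.

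It can also be said that 1000 draws do not invalidate the test, that the error matters only for true p between about 0.04 and 0.06, and that these tests supplement the visual and descriptive analyses. All of this is correct and limits the importance of the point. It does not remove it: the number 1000 is stated, and the seed dependence near the cut-off follows from it under either counting rule.

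**Conclusion.** The point holds as a minor one. With the stated 1000 draws, an individual p-value near 0.05 has a standard error of about 0.007 and lands on the wrong side in 20% of runs at a true p of 0.045 and 27% at 0.055, against about 1% with 10,000 draws. This assumes a 0.05 cut-off. The consequence is that a small share of participants' verdicts depend on the seed.

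The zero p-value is conditional on the literal count being used. It then costs about 0.001 in size, and becomes serious only under a product-type group rule, which the protocol neither names nor excludes. The documents do not support a claim that the efficacy conclusion is wrong.

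**What to change.** In section 10.3.2, replace the 1000 draws with at least 10,000 random permutations and a recorded seed, or full enumeration where few arrangements remain after distancing. State the p-value as (count + 1)/(permutations + 1), and say that these p-values enter the group combination. Naming the combination formula in the same place would settle the conditional part. If the app is fixed at 1000 draws, the same test can be run from a short script.

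The cost is one or two sentences and seconds of computing. The +1 raises p-values by at most about 0.001 at 1000 draws, and by less with more. Nothing changes for participants or data collection.

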The Social Isolation Short Form 4a, derived from the more extensive UCLA Loneliness Scale, is a globally recognized tool for measuring loneliness. It aligns with the UK's Office for National Statistics recommendations for assessing loneliness (ONS, 2018) and has demonstrated reliability in gauging social isolation. Although a more detailed version, the Social Isolation Short Form 8a, is available and offers increased reliability, its length might be burdensome for weekly assessments. Therefore, this study proposes using the shorter form as a primary outcome. It will be administered weekly, following each individual therapy session.

Service use

To determine if there is any potential cost saving for the NHS, we will ask participants to consent to the research team to take a record of:

- Unplanned contact with the service
- A and E attendances
- Crisis line contacts
- Days in psychiatric hospital
- Days spent in general hospital

Self harm and suicidal behaviour

To determine if there has been any reduction in self-harm and suicidal behaviour, we will ask participants to consent to the research team to take a record of:

- Incidents of self-harm recorded in the clinical record
- Incidents where the participant has engaged in self-injury or self-neglect where their intent was to cause life threatening injury.

3.2 Secondary Outcome:

Other Routine Outcome Measures: Quality of Life, Patient Satisfaction, and Suicidality

In addition to the weekly assessments, participants will complete three other questionnaires at start of baseline, start of treatment, 6 months, 12 months, 18 months into the treatment and at the end of follow-up. These scales evaluate quality of life (ReQol), patient satisfaction (Dialogue), and suicidality (Columbia Scale).

*ReQoI: The Recovering Quality of Life (ReQoI-10) scale tracks perceived changes in 'quality of life' over time. This 10-item scale is validated for individuals aged 16 and above. Scores range between 1 and 5, and a shift of 5 points on the scale indicates 'significant improvements' (Keetharuth et al., 2018).

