3.3 Outcome measures/endpoints

The endpoint for the study's outcome will be at 24 months. This will include 18 months of treatment, and 6 months of follow up.

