3.4 Primary endpoint/outcome

Reductions in the LPFS 2.0 and Social Isolation short form 4.0 constitute a potential benefit. We have chosen these outcome measurements as they are used internationally, recommended by ICHOM, and have been validated for use in older adults. We are measuring personality functioning and social isolation as our primary measures. We are making comparisons between baseline functioning, and across participants to power the study. Measurements are taken weekly from start of the waiting period, for the duration of the treatment phase, and at follow up.

The primary endpoint will be whether personality function (as measured by the LPFS 2.0) and social isolation (as measured by the social isolation short form 4.0) have changed during 24 months. Significant decreases in both measures will indicate that MBT is effective at improving personality functioning and decreasing social isolation.

Additionally, if participants had any incidents of suicidal behaviour or self-harm, then a reduction in frequency of these events will constitute a potential benefit. As older people may keep suicidal behaviour and self-harm hidden, there is an expectation that participants may not make disclosures around these issues at baseline.

Taking data pertaining to service use may provide a limited indication as to whether any potential cost savings are associated with the intervention. Due to the limited number of participants, there is a recognition that statistical test on these findings may not reach statistical significance.

Any reduction in self-harm, suicidality, or service use may also represent efficacy.

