3.7 Table of endpoints/outcomes

Objectives	Outcome Measures	Timepoint(s) of evaluation of this outcome measure (if applicable)
Primary Objective Personality Functioning Social isolation	LPFS 2.0. Social Isolation Short Form 4.0	Both questionnaires are given from day 0 till the end of data collection period at 24 months. Patients are requested to fill out these two questionnaires on a weekly basis during waiting period, treatment and follow up.
Service use Self injury and suicidal behaviour	Service use Suicidal behaviour	Data to be taken from clinical records at 0,6,12,18, and 24 months
Feasibility	Comparison of recruitment rate, drop out, and completion	Data to be taken at 0, 6, 12, 18, 24 months
Acceptability	Thematic analysis of qualitative interview	Analysis of data at 24 months
Secondary Objectives		
To evaluate	ReQoL 10	Measures provided at 6 month
quality of life (ReQol),		intervals, at 0,6,12,18, and 24 months.
patient satisfaction (Dialogue),	Dialogue	months.
and suicidality (Columbia Scale).	CSRSS (Columbia Scale)	

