4 TRIAL DESIGN

Design:

This study uses a multiple single case series design, a form of Single Case Design (SCD). It will employ quantitative methods to track changes in personality functioning over time using the LPFS 2.0 scale and changes in loneliness using the Social Isolation Short Form 4a. Data from a participant will be compared within the participant between treatment phases (baseline, treatment and follow up), so participants serve as their own controls. Initial data collection will take place at an outpatient clinic in Manchester, United Kingdom. Data will be gathered weekly away from the MBT clinic. The research team, primarily involved in clinical practice, will utilize an established older adult MBT service in Manchester for the sample. This approach mitigates some challenges of assessing multi-modal

psychological treatments, as there's no need for the research team to establish a new therapy program.

A multiple single case series design will enhance experimental control since participants serve as their own control. In order to get a stable and representative estimate of the baseline state all participants will have a waiting period of 8 weeks before starting treatment. Participants who drop out of the research completely during this phase won't have any further data collected We will ask anyone who drops out of the therapy to consent to providing data relating to their reason for drop out.

The strength of a SCD study is that it produces statistical power by taking a large number of data points with a small number of participants. Due to the high number of data points per participant, change to outcome measurements can accurately be described. Additionally, due to the low number of participants, there is a lower cost to the intervention, which means that it is more feasible to carry out long term studies of psychological treatments for personality disorder, which often span multiple years.

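### Service-use and self-harm counts are compared between phases of about 2, 18 and 6 months with no adjustment for time at risk, and the six-monthly extraction that could avoid this is not tied to the phases

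*Protocol*

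**What the plan says.** Section 3.1 of the protocol lists five service-use items and two self-harm items among the primary outcomes. All are counts of events or of days, for example "Incidents of self-harm recorded in the clinical record" and "Days in psychiatric hospital".

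Section 10.3.2 fixes the comparison and the test: "Service use and self-harm data will be compared between the treatment phases with nonparametric test for repeated measures (Friedman Test"), with a parametric test allowed if its requirements are met. Section 4 says that data are compared "within the participant between treatment phases (baseline, treatment and follow up"), and section 10.3.1 repeats this. On length, section 4 states that "all participants will have a waiting period of 8 weeks before starting treatment". Section 3.3 puts the endpoint at 24 months and adds: "This will include 18 months of treatment, and 6 months of follow up".

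Section 3.7 gives the extraction schedule: "Data to be taken from clinical records at 0,6,12,18, and 24 months". Section 7.3 takes baseline service-use and self-harm data without saying what period they cover. Section 3.4 describes fewer self-harm or suicidal events as a potential benefit and ends: "Any reduction in self-harm, suicidality, or service use may also represent efficacy".

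**The concern.** A count depends on how long one counts. Section 10.3.2 sets counts from phases of very different length side by side and mentions no rate, offset or common window. A rank test on such totals responds to the calendar as well as to the treatment. These data are the only quantitative support for the cost-saving hypothesis on the title page and the main support for the risk-reducing one, and section 3.4 sets no threshold for what reduction is of interest.

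The six-monthly extraction could supply equal windows, but the protocol does not say that the test uses them. If the windows are chosen after the counts have been seen, the direction of the result can turn on that choice. Section 3.4 also expects some participants not to disclose self-harm at baseline, which would lower an already short baseline count further.

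**Working it through.** **The plan's own figure.** The only computed figure is in section 10.1: power close to 1 with 10 participants and Cohen's d of 1. It concerns the weekly scales. A simulation with 8 baseline and 72 treatment observations per participant and an approximate version of the permutation test gave group power of 1.00 at autocorrelation 0 to 0.5 and 0.98 at 0.7. The figure therefore reproduces, but it says nothing about event counts.

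**Step 1: exposure.** Baseline is 8 weeks = 56 / 30.44 = 1.84 months (section 4). Treatment is 18 months and follow-up 6 months (section 3.3). With a constant rate r, the expected total is r × months:
- treatment / baseline = 18 / 1.84 = 9.8
- follow-up / baseline = 6 / 1.84 = 3.3
- follow-up / treatment = 6 / 18 = 0.33, an apparent fall of two thirds
- with a true halving during treatment, treatment / baseline = 0.5 × 9.8 = 4.9, still an apparent rise. At 1 event per 6 months and n = 10, the treatment total exceeds the baseline total in about 99% of trials.

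**Step 2: do the extraction dates match the phases?** Waiting period, treatment and follow-up add up to 1.84 + 18 + 6 = 25.84 months, but section 3.7 ends at 24. Its row for the weekly scales starts at day 0 and includes the waiting period.
- If day 0 is the start of waiting, the 0-6 window holds 1.84 months of baseline and 4.16 of treatment. The 18-24 window holds 1.84 months of treatment and 4.16 of follow-up, and the last 1.84 months of follow-up are not covered.
- If day 0 is the start of treatment, as section 3.3 implies, the later windows fit the phases, but the month-0 extraction has no stated length.

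**Step 3: false rejection with no change in rate.** Friedman test, nominal level 0.05, n = 10, 3,000 runs. The protocol gives no event rate, so the rates and the level are assumptions. In each cell the first figure is for Poisson counts and the second adds gamma variation between participants (shape 1).

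| Events per month (per 6 months) | Mean counts by phase | Phase totals | 8-week baseline and four 6-month windows | Five equal 6-month windows | Phase totals divided by phase length |
|---|---|---|---|---|---|
| 0.05 (0.3) | 0.09 / 0.9 / 0.3 | 0.59; 0.49 | 0.08; 0.06 | 0.03; 0.03 | 0.33; 0.22 |
| 0.1 (0.6) | 0.19 / 1.8 / 0.6 | 0.88; 0.77 | 0.18; 0.14 | 0.04; 0.04 | 0.32; 0.20 |
| 0.2 (1.2) | 0.37 / 3.6 / 1.2 | 0.99; 0.93 | 0.39; 0.31 | 0.04; 0.05 | 0.16; 0.15 |
| 0.5 (3) | 0.93 / 9.0 / 3.0 | 1.00; 0.99 | 0.86; 0.67 | 0.04; 0.04 | 0.06; 0.09 |

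Over 0.3 to 2 events per 6 months, and allowing stronger variation between participants, the ranges are about 42-100% for phase totals, 6-65% for an 8-week baseline against 6-month windows, and 3-5% for equal windows. The last row of the table lies above that range of rates. With phase totals, the group count rises from baseline to treatment in 99-100% of runs and falls from treatment to follow-up in 94-100%.

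The last column shows that converting to rates and keeping the Friedman test does not repair sparse counts. A short phase mostly yields a rate of zero, so the ranks still depend on phase length.

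**The case against.** The strongest reply is that the protocol never says events are summed over whole phases. Sections 3.7, 7 and 7.4 take these data every six months, which splits treatment into three windows equal to the follow-up window. On that reading the two-thirds fall does not arise. Section 10.3.3 uses the same wording about phases, with the same test, for questionnaires given on dated occasions, so the wording may be loose. The three-phase sentence in sections 4 and 10.3.1 follows a description of the weekly scales. A month-0 record extraction could look back 6 months, and false rejection would then return to 3-5%. All of this stands: phase totals are the natural reading of section 10.3.2, not the only one. What remains is that the look-back and the mapping are unstated, and that a baseline limited to 8 weeks still produces a false increase.

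A reader might infer that the plan counts any reduction as efficacy. It does not. Section 3.4 says a reduction may represent efficacy or a potential benefit, calls the service-use evidence limited, and can be read as meaning a rate where it speaks of the frequency of self-harm events. A reader might also infer a general bias in favour of MBT. Even with phase totals, both comparisons with baseline are biased against MBT, and only treatment to follow-up favours it.

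The caveat in section 3.4 that tests on service use may not reach significance does not answer the point. It concerns low power, whereas the risk here is significance produced by unequal exposure.

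**Conclusion.** The concern holds as a fault in how the comparison is specified. Read naturally, section 10.3.2 yields a wrong result: at an unchanged rate, totals of about 1 : 9.8 : 3.3 and rejection in about 42-100% of trials with n = 10. Read together with section 3.7, with only the baseline short, it yields a false increase in about 6-65% and no false later benefit. With a 6-month look-back and equal windows the problem disappears.

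The exposure ratios rest only on the protocol's phase lengths. The rejection rates rest on assumed rates of 0.3 to 2 events per 6 months, a 0.05 level and a constant rate within each participant. The documents do not support saying that phase totals will certainly be used, or that a false claim of efficacy would follow.

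**What to change.** In sections 10.3.2 and 3.7, define day 0 and compare equal 6-month windows: a 6-month look-back from a stated anchor, months 0-6, 6-12 and 12-18 of treatment, and the 6 months of follow-up. State how the 12-week introductory group and the 8-week waiting period are assigned. If the phases run without gaps, a look-back anchored at the start of treatment would contain 2.76 + 1.84 = 4.60 months of these and only 1.40 months before them.

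Alternatively, replace the Friedman test for these counts with a Poisson or negative-binomial repeated-measures model with a log person-time offset, and report rate ratios with confidence intervals. Do not simply feed rates into the Friedman test.

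In section 3.4, replace the sentence "Any reduction in self-harm, suicidality, or service use may also represent efficacy" with a descriptive statement about change in event rate per unit of time.

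The cost is protocol wording, one look-back in records already being accessed, and cover for it in the consent text. No extra visits are needed. With 10-14 participants the intervals will be wide, and the report should say so.
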